## 1 Abbreviations and Definitions

AE	Adverse Event
CF	Colonization Factors
CRF	Case Report Form
dmLT	Double Mutant Heat-Labile Toxin
ETEC	Enterotoxigenic E. coli
ID	Intradermal
LT	Heat Labile Enterotoxin
SAP	Statistical Analysis Plan
ST	Heat Stable Enterotoxin
Tukey's HSD	Tukey's HSD (Honestly Significant Difference) test

## 2 Introduction

Worldwide, diarrhea causes approximately 1.7 billion cases annually [1]. In developing countries, there is recognition of the disease burden and in many cases, significant efforts have been made to improve sanitation, nutrition, and treatment management. However, diarrhea related complications still results in approximately 760,000 deaths in children annually, with the highest numbers in those younger than two years of life [1, 2]. The recognized need for more early effective countermeasures has driven a number of research agendas, including the development of enteric vaccines.

ETEC, one of several pathotypes of diarrheagenic *E. coli*, causes a secretory diarrhea that can range in presentation from mild discomfort to cholera-like purging. It is the most prevalent bacterial cause of childhood diarrhea in developing countries, and while the estimated number of ETEC episodes and deaths vary among researchers, in one estimate, ETEC was thought to cause 210 million cases of diarrhea and 380,000 deaths annually among infants and young children [3-7]. ETEC illness in the young has also been associated with growth faltering [8], and the repeated episodes caused by this infection are likely to lead to declines in both physical and cognitive development [9], which in turn are considered to have attendant macroeconomic consequences in countries and regions most heavily afflicted [10]. It is also the leading cause of travelers' diarrhea, etiologically implicated in 30-50% or more of cases [11-14], and this may be markedly underestimated due to the insensitivity of testing methods [15]. Its dual importance in global public health and military/travel medicine has galvanized policy makers in both sectors to develop a safe, effective ETEC vaccine, though such efforts remain under-resourced.

ETEC express adhesive fimbriae [also known as colonization factors (CFs)], surface-exposed polymeric protein appendages that plays a vital role in the initial step of ETEC pathogenesis. CFs mediate initial ETEC adherence to, and colonization of, the small intestine, after which ETEC secrete one or both of two enterotoxins that induce fluid and electrolyte secretion resulting in watery diarrhea. The two enterotoxins produced by ETEC are heat-stable enterotoxin (ST) and heat-labile enterotoxin (LT). CFs have long been a prime target for vaccine research and development. Their role as protective antigens has been substantiated by a number of studies in populations naturally exposed to ETEC diarrhea as well as volunteer studies of experimentally induced diarrhea, as has the role of LT enterotoxin [16-20]. Evidence for the preventive role of anti-CF immunity also derives from studies showing that bovine milk antibody product with high antibody titers against ETEC, and more specifically, purified colonization factor antigens, provided protection to humans in challenge studies [21, 22]. To date, more than twenty-two serologically distinct CFs have been identified.

CS6 is an atypical polymeric antigen that is highly prevalent among ETEC disease isolates from various geographic regions [20, 23, 24]. It is a heteropolymer composed of two structural subunits, CssA and CssB, in a ca. 1:1 ratio that has been confirmed with publication of the CssA and CssB crystal structures [25]. Recent reports provide evidence that CS6 binds to the human intestinal cell lines Caco-2 and INT407 [26, 27], consistent with the adhesive role that CS6 is presumed to play in ETEC disease pathogenesis. Jansson et al. reported that purified CS6 and recombinant CssB fused to glutathione-S-transferase (GST) were both shown to bind to intestinal glycosphingolipid sulfatide by thin layer chromatography [28].

Given the relatively high global prevalence of CS6-ETEC, we view the development of a protective, recombinant derivative of CS6 as critical to our overall strategy to develop a broadly protective multivalent ETEC adhesin subunit vaccine. As such, with the current data known, development of the prototype CS6 adhesin-based vaccine began with the development and characterization of *in cis* donor strand complemented variants of CssA (dsc16CssA[His]6, referred to as dscCssA) and CssB (dsc16CssB[His]6, referred to as dscCssB). Based on multiple lines of evidence, ntd14dsc16BCssBA (a variant of the original dscCssBA in which the N-terminal 14 amino acids has been removed and a heterologous CssB-derived donor strand is used to complement the C-terminal CssA), here after termed CssBA, was selected as the lead vaccine prototype. This product was assessed serially in a mouse immunogenicity model and an *A. nancymaae* NHP vaccination-challenge model. We then scaled up fermentation and purification processes, in preparation for bioproduction under cGMP conditions. Subsequent mouse immunogenicity studies of the cGMP CssBA lot demonstrated similar anti-CS6 IgG response to that of the research grade lot.

### 3 Analytical Methods

For nominal outcomes, parameter estimates will be calculated with 95% confidence intervals utilizing valid asymptomatic and/or exact binomial estimates. For continuous outcomes, measures of central tendency will be estimated based on the data distribution. Data following a Gaussian distribution (or data for which the central limit theorem appear applicable) will be summarized across study groups using a mean and standard deviation (and/or 95% confidence intervals). Continuous data which are not normally distributed (or for which the central limit theorem is not applicable) and ordinal data will be summarized across study groups using a median and interquartile range. Data transformations will be applied to approximate a Gaussian distribution as applicable. In particular, titers will be log-transformed prior to statistical comparisons and log10-transformed means (and standard deviations) and/or geometric mean titers will be estimated.

In general, between-cohort comparisons will be examined with nonparametric tests (Kruskal-Wallis for continuous data and Fisher's exact test for categorical data) unless assumptions are fulfilled for Analysis of Variance (ANOVA) or Pearson's  $\chi^2$ .

Importantly, this study is designed to enable estimates of clinical, immunological, and microbiological endpoints not to compare parameter estimates across study cohorts. Nonetheless, these comparisons across cohorts will be made and guided by an Omnibus null hypothesis as follows (where  $\theta$  is any nominal, continuous or ordinal parameter):  $\theta_{\text{Cohort A}} = \theta_{\text{Cohort B}} = \theta_{\text{Cohort C}} = \theta_{\text{Cohort D}}$

Post-hoc comparisons will include the following: Bonferonni, Sidak, Tukey's HSD or Newman-Keuls.

Additionally, nonparametric paired *t* tests (Wilcoxon paired signed rank test) may be used to compare continuous data at two separate time points unless assumptions are fulfilled for paired *t*-test. Additional

comparisons may include repeated measures analysis of variance with study group as the between subject factor and sample collection time-points as the repeated factor.

All statistical tests will be interpreted in a two-tailed fashion using an  $\alpha = 0.05$ .

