## **5 Study Methods**

This is an open-label Phase 1 clinical trial of CssBA±dmLT in which a total of 50 subjects will receive three vaccinations via IM injection on days 1, 22, and 43 (See Table 2). Dose escalation of CssBA from 5µg to 15µg to 45µg, and dmLT from 100 to 500ng will take place as outlined below. Group A is considered a pilot group in which CssBA and dmLT will be administered separately. All 3 doses will be administered and subjects monitored for safety 7 days after the third vaccination, prior to the enrollment of subjects in Group B.

The decision to advance to the next group will be based solely on the safety assessment. A dose level with no occurrence of stopping criteria will prompt moving to the next higher level. All safety data will be summarized and reviewed with the SRC prior to advancing to dose escalation.

Approximately one week after the first group (Group A) receives the third vaccination dose (Day 49), an interim Safety Report will be prepared by the PI and Study Statistician for review by the SRC. The content of the report will be agreed upon by the PI and the SRC and will include, but not be limited to, all adverse events (solicited, unsolicited, expected and unexpected) as well as relevant safety endpoints. Advancement to Group B will be based entirely on this safety assessment. The SRC's concurrence to advance to the next group will be made and provided in written format. This process will be repeated after groups B, C, and D before enrollment for the next group.

dmLT will be administered at the 500 ng dose in groups D and E if no significant reactogenicity is observed in Group C.

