## **8 Immunology Analyses**

Analyses will include both qualitative (responder rates) and quantitative outcomes.

Graphical displays of immune responses will include the following:

- 1) Serum IgG and IgA responses to LT and CS6
- 2) Antibody Lymphocyte Supernatants (ALS) responses to LT and CS6

Between-group comparisons will be examined with nonparametric tests (Kruskal-Wallis for continuous data and Fisher's exact test for categorical data) unless assumptions are fulfilled

for Analysis of Variance (ANOVA) or Pearson's  $\chi^2$ . Nonparametric paired *t* tests (Wilcoxon paired signed rank test) will be used to compare individual post-challenge to pre-challenge response within each treatment group unless assumptions are fulfilled for paired *t*-test. Comparisons of ALS responses post-vaccination will be performed using the Kruskal-Wallis test. All statistical tests will be interpreted in a two-tailed fashion using  $\alpha = 0.05$ . Statistical analyses will be performed using SAS v9.x for Windows (The SAS Institute, Cary, NC).

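### The post-hoc list admits Newman-Keuls, which does not control familywise error when only some cohorts are equal, and ties none of the listed methods to the test it follows

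*SAP*

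**What the plan says.** SAP section 3 (Analytical Methods) sets the default: "between-cohort comparisons will be examined with nonparametric tests (Kruskal-Wallis for continuous data and Fisher's exact test for categorical data) unless assumptions are fulfilled" for ANOVA or Pearson's chi-square. Section 8 (Immunology Analyses) repeats this default and names no post-hoc method.

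On comparisons between cohorts, section 3 says that "these comparisons across cohorts will be made and guided by an Omnibus null hypothesis as follows", and then writes the hypothesis for Cohorts A to D only. The follow-up is one sentence: "Post-hoc comparisons will include the following: Bonferonni, Sidak, Tukey's HSD or Newman-Keuls". Nothing in the SAP says which method goes with which test, endpoint or set of pairs. Elsewhere, Tukey's HSD appears only in the abbreviation list.

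On the error level: "All statistical tests will be interpreted in a two-tailed fashion using an" alpha of 0.05. That is a level per test; no familywise level is given.

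On the number of groups, Table 2 in section 5 has five lettered groups, A to E. Of Group A the SAP says: "Group A is considered a pilot group in which CssBA and dmLT will be administered separately". Table 2 gives its two arms 5 subjects each, and the results tables in section 9 mostly show them as A-1 and A-2, which makes six cells.

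**The concern.** A post-hoc procedure is named in order to limit false positive pairwise findings. Newman-Keuls does this only when every cohort is equal. Once some cohorts truly differ, it tests each remaining set of equal cohorts almost separately, and the chance of at least one false difference grows with the number of such sets. Omnibus screening does not help, because the omnibus hypothesis is then rightly rejected.

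Two further features make the sentence hard to apply. Tukey's HSD and Newman-Keuls use means, a pooled variance and the studentized range, so they are not follow-ups to a rank test or an exact test on proportions. And because the four names are joined by an open choice, a pair could be called different under one method and not under another, with the method chosen after the data are seen.

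At stake are the pairwise statements about titers, responder rates and adverse event rates in the final report.

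**Working it through.** The SAP gives no familywise figure, effect size or SD for these comparisons, so there is no figure of its own to reproduce. All mean patterns below are assumptions.

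**Inputs.** Alpha 0.05, two-sided (section 3). Group sizes from Table 2: A-1 = 5, A-2 = 5, B to E = 10 each, total 50. Number of groups k: 4 in the written omnibus hypothesis, 5 lettered groups, 6 reporting cells.

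**Worst case.** If the means fall into m well-separated sets, each with at least two equal cohorts, the Newman-Keuls familywise error is about 1 − 0.95^m. The largest possible m is k/2 rounded down.
- k = 4 or 5, m = 2: 1 − 0.95² = 1 − 0.9025 = 9.75%.
- k = 6, m = 3: 1 − 0.95³ = 1 − 0.857375 = 14.3%.

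**Simulation of the worst case** (20,000 runs per setting, normal data, pooled variance, Tukey-Kramer standard errors; 10 per group for k = 4 and 5, and 5, 5, 10, 10, 10, 10 for k = 6):

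| Setting | Newman-Keuls | Tukey | Bonferroni |
|---|---|---|---|
| k = 4, two equal pairs | 9.8% | 1.9% | 1.6% |
| k = 5, two equal pairs and one other | 9.7% | 1.4% | 1.0% |
| k = 6, three equal pairs | 13.7% | 1.4% | 1.0% |
| k = 6, three equal pairs, 2 SD apart | 14.1% | 1.4% | 1.1% |
| k = 5, all equal | 5.2% | 5.2% | 4.0% |
| k = 6, all equal | 4.5% | 4.8% | 3.4% |

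**Patterns based on Table 2** (k = 6, actual group sizes, well-separated sets):
- Equal by CssBA dose: A-1, B and C share 5 µg; A-2, D and E each stand alone. Here m = 1, so about 5%; simulated 4.6 to 4.8%.
- Equal by dmLT dose, with D and E at 500 ng: A-2 and B share 100 ng; C, D and E share 500 ng; A-1 stands alone. Here m = 2, so at most 9.75%; simulated 9.6%.
- Equal by dmLT dose, with D and E at 100 ng: A-2, B, D and E form one set. Here m = 1, so about 5%. The SAP leaves this open: "dmLT will be administered at the 500 ng dose in groups D and E if no significant reactogenicity is observed in Group C".

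Tukey-Kramer stays at about 1 to 2% under the first two patterns.

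**How much the open choice matters.** The smallest difference declared significant between two arms of 10, in SD units, with 50 − 5 = 45 or 50 − 6 = 44 degrees of freedom, is t × √(2/10) for Newman-Keuls on adjacent means (unadjusted t, once the wider ranges are rejected) and for Bonferroni (adjusted t), and q/√10 for Tukey:
- Five groups: 0.90 (Newman-Keuls), 1.27 (Tukey), 1.32 (Bonferroni over 10 pairs, 0.05/10 = 0.0050).
- Six cells: 0.90, 1.33, 1.39 (Bonferroni over 15 pairs, 0.05/15 = 0.0033).

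An adjacent-pair difference of 0.9 to 1.3 SD can therefore be significant or not, depending on the method picked.

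**Fit to the test.**

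| Test used | Listed methods that can follow it |
|---|---|
| ANOVA on log10 titers | all four in type; Newman-Keuls without strong error control |
| Kruskal-Wallis | Bonferroni or Sidak on pairwise rank p-values |
| Fisher's exact or Pearson's chi-square | Bonferroni or Sidak on pairwise p-values |

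**The case against.** The SAP promises no familywise level. Section 3 presents the study as one for estimation, and section 6 says that it was not sized to show differences between groups. In an open-label Phase 1 study of 50 subjects, loose multiplicity control is a limited fault. This stands, and it sets the weight of the point. A reader might infer that a stated 5% familywise level is breached; the document states 0.05 per test only.

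A reader might also take 14% as the error to expect. It needs three equal, well-separated pairs among the six cells, which neither dose in Table 2 produces. The patterns that Table 2 does suggest give about 5% or about 10%.

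A further inference would be that post-hoc p-values settle the dose for the later challenge trial. Section 4.2 lists identifying a dose among the secondary objectives, but no section says that pairwise tests decide it. Section 5 rests advancement between groups on safety alone, and section 6 foresees larger follow-on studies.

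Finally, the list can be read as one menu for both the parametric and the nonparametric branch, since Bonferroni and Sidak suit rank and exact p-values. That is fair: it would be wrong to say that nothing listed fits the default tests. What is missing is the rule that links method to test. None of these replies defends Newman-Keuls, which fails at the one task for which the list exists.

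**Conclusion.** The point holds in a limited form. Newman-Keuls is a permitted method whose familywise error reaches about 10% with four or five groups and 14% with six cells at worst, and about 5% or 10% under dose-based patterns, against 1 to 2% for Tukey-Kramer under those patterns. These figures assume normal data, a common variance and well-separated means; the mean patterns are not in the SAP. The mismatch with the default tests applies to Newman-Keuls and Tukey's HSD, not to Bonferroni or Sidak. The open choice of method would by itself be only missing detail. The consequence is confined to exploratory pairwise statements; the descriptive safety summaries for the primary objective are untouched.

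**What to change.** In section 3, replace the post-hoc sentence with one rule per test:
- Delete Newman-Keuls.
- After ANOVA on log10 titers, use Tukey-Kramer, because A-1 and A-2 have 5 subjects each and the other groups 10.
- After Kruskal-Wallis, Fisher's exact test or Pearson's chi-square, apply Bonferroni or Sidak (name one) to the pairwise rank or Fisher p-values. Holm is an optional, more powerful alternative.
- State how many groups or cells are compared and which pairs form the family, and refer to the rule in section 8.

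The cost is SAP wording and slightly fewer pairs declared different. The choice of family matters most for the arms of 5: an exact two-sided comparison of A-1 with A-2 cannot give a p-value below 2/252 = 0.0079 (252 ways to split 10 subjects into 5 and 5), so it can never pass 0.0033 if all 15 pairs are adjusted by Bonferroni. Limiting the family to the pairs of interest, or using Holm, eases this.

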## **4 Study Objectives**

### **4.1 Primary Objectives**

- Evaluate the safety of CssBA ± dmLT given by IM injection

### **4.2 Secondary Objectives**

- Evaluate immune responses following IM vaccination with CssBA ±dmLT
- Identify a safe and immunogenic dose and route of a CssBA-based vaccine to be used in a subsequent vaccine and experimental challenge trial

These exploratory objectives are beyond the scope of the SAP.

## **5 Study Methods**

This is an open-label Phase 1 clinical trial of CssBA±dmLT in which a total of 50 subjects will receive three vaccinations via IM injection on days 1, 22, and 43 (See Table 2). Dose escalation of CssBA from 5µg to 15µg to 45µg, and dmLT from 100 to 500ng will take place as outlined below. Group A is considered a pilot group in which CssBA and dmLT will be administered separately. All 3 doses will be administered and subjects monitored for safety 7 days after the third vaccination, prior to the enrollment of subjects in Group B.

The decision to advance to the next group will be based solely on the safety assessment. A dose level with no occurrence of stopping criteria will prompt moving to the next higher level. All safety data will be summarized and reviewed with the SRC prior to advancing to dose escalation.

Approximately one week after the first group (Group A) receives the third vaccination dose (Day 49), an interim Safety Report will be prepared by the PI and Study Statistician for review by the SRC. The content of the report will be agreed upon by the PI and the SRC and will include, but not be limited to, all adverse events (solicited, unsolicited, expected and unexpected) as well as relevant safety endpoints. Advancement to Group B will be based entirely on this safety assessment. The SRC's concurrence to advance to the next group will be made and provided in written format. This process will be repeated after groups B, C, and D before enrollment for the next group.

dmLT will be administered at the 500 ng dose in groups D and E if no significant reactogenicity is observed in Group C.

**Table 2. Study Design of Phase 1 Clinical Trial of Intramuscularly Administered CssBA with dmLT (N=50)**

Group	N	Route	CssBA (µg)	dmLT (ng)
A	5	IM	5	0
	5	IM	0	100
B	10	IM	5	100
C	10	IM	5	500
D*	10	IM	15	100/500
E*	10	IM	45	100/500

\*Plan to proceed with 500ng dose; however, if there is an aberrant safety signal in Group C, will proceed with the 100 ng dose (presuming no prior signal in Group B)

## **5.1 Inclusion-Exclusion Criteria**

### **5.1.1 Inclusion Criteria**

Subjects must meet all of the following criteria to be included in the study:

1. Healthy, adult, male or female, age 18 to 45 years (inclusive) at the time of enrollment
2. Completion and review of comprehension test (achieved  $\geq 70\%$  accuracy).
3. Signed informed consent document
4. Available for the required follow-up period and scheduled clinic visits.
5. Women: Negative pregnancy test with understanding (through informed consent process) to not become pregnant during the study or within three (3) months following last vaccination

### **5.1.2 Exclusion Criteria**

#### *General health criteria*

1. Health problems (for example, intercurrent febrile illness, chronic medical conditions such as psychiatric conditions, diabetes mellitus, hypertension or any other conditions that might place the subject at increased risk of adverse events-study clinicians, in consultation with the PI, will use clinical judgment on a case-by-case basis to assess safety risks under this criterion. The PI will consult with the Research Monitor as appropriate.
2. Clinically significant abnormalities on physical examination
3. Immunosuppressive drugs (use of systemic corticosteroids or chemotherapeutics that may influence antibody development) or illness (including IgA deficiency, defined by serum IgA  $<7$  mg/dL).
4. Women who are pregnant or planning to become pregnant during the study period plus 3 months beyond the last vaccination and currently nursing women

5. Participation in research involving another investigational product (defined as receipt of investigational product or exposure to invasive investigational device) 30 days before planned date of first vaccination or anytime through the last study safety visit.
6. Positive blood test for HBsAg, HCV, HIV-1/2
7. Clinically significant abnormalities on basic laboratory screening

#### *Research Specific*

1. Exclusionary skin history/findings that would confound assessment or prevent appropriate local monitoring of AEs, or possibly increase the risk of an AE.
2. History of chronic skin disease (clinician judgment)
3. Acute skin infection/eruptions on the upper arms including fungal infections, severe acne or active contact dermatitis
4. Allergies that may increase the risk of AEs
5. Regular use (weekly or more often) of antidiarrheal, anti-constipation, or antacid therapy
6. Abnormal stool pattern (fewer than 3 stools per week or more than 3 stools per day) on a regular basis; loose or liquid stools on other than an occasional basis

#### *Prior exposure to ETEC or Vibrio cholerae*

1. History of microbiologically confirmed ETEC or cholera infection in the last 3 years
2. Travel to countries where ETEC or *V. cholerae* or other enteric infections are endemic (most of the developing world) within 3 years prior to dosing (clinician judgment)
3. Symptoms consistent with Travelers' Diarrhea concurrent with travel to countries where ETEC infection is endemic (most of the developing world) within 3 years prior to dosing, OR planned travel to endemic countries during the length of the study
4. Vaccination for or ingestion of ETEC, cholera, or *E. coli* heat labile toxin within 3 years prior to dosing
5. Occupation involving handling of ETEC or *V. cholerae* currently, or in the past 3 years

